5.5 Statistical models

5.5.1 Primary analysis

The statistical hypothesis for the GLOESS being tested is that there is no difference in the mean change from baseline scores over 12 weeks in the secukinumab regimen vs the placebo regimen.

The model to be tested is as follows:-

Change from baseline in GLOESS = Treatment + center + analysis visit + weight + baseline GLOESS + Treatment * analysis visit.

The procedure PROC MIXED will be used to perform the MMRM analysis. Treatment regimen, center and analysis visit will be set as class variables. The model statement will be based on the formula outlined above. The repeated statement of PROC MIXED will set analysis visit as the repeated variable and the type option will set the convergence method. An unstructured covariance structure will be assumed for this model (type=UN). If the model does not converge, the compound symmetry covariance structure will be used (type=CS). The data will be assumed to be missing at random (MAR). The overall method will be set to REML.

From this analysis, the adjusted changes for each treatment group, the difference between the adjusted changes (secukinumab group vs placebo), 95% confidence interval around the difference and 1-sided p-value will be calculated for each visit.

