2.5.2 Statistical hypothesis, model, and method of analysis

The statistical hypothesis for the GLOESS being tested is that there is no difference in the mean change from baseline scores over 12 weeks in the secukinumab regimen vs the placebo ± MTX (and non-biologic DMARDs) regimen.

Between-treatment differences in the change in GLOESS will be evaluated using a mixed-effect model repeated measures model (MMRM) with treatment regimen, center and analysis visit as factors and weight and baseline GLOESS as continuous covariates. Treatment by analysis visit will be included as an interaction term in the model. An unstructured covariance structure will be assumed for this model. If the model does not converge, the compound symmetry covariance structure will be used. The data will be assumed to be missing at random (MAR).

[figure not shown]

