Response at Week 12 in ACR 20 in the FAS will be evaluated using a logistic regression model with study treatment as a factor and baseline weight as a covariate. The odds ratios will be computed for comparison of secukinumab versus placebo using the logistic regression model fitted. In cases where separation is a concern for secondary endpoint at Week 12 an exact logistic regression model will be applied to all visits. To ensure convergence, this model will not include any continuous covariates. When exact logistic regression is unable to be implemented then Fisher's exact test will be applied. In this case no odds ratios or confidence intervals can be estimated but p-values may be calculated.

ACR 50 at Week 12

Response at Week 12 in ACR 50 in the FAS will be evaluated using a logistic regression model with study treatment as a factor and baseline weight as a covariate. The odds ratios will be computed for comparison of secukinumab versus placebo using the logistic regression model fitted. In cases where separation is a concern for secondary endpoint at Week 12 an exact logistic regression model will be applied to all visits. To ensure convergence, this model will not include any continuous covariates. When exact logistic regression is unable to be implemented then Fisher's exact test will be applied. In this case no odds ratios or confidence intervals can be estimated but p-values may be calculated.

Changes in SPARCC at Week 12

Between-treatment differences in the change from baseline in SPARCC at Week 12 in the FAS will be compared by means of a MMRM with treatment regimen and analysis visit as factors and baseline weight and SPARCC score as continuous covariates. Study treatment by analysis visit will be included as an interaction term in the model. An unstructured covariance structure will be assumed for this model. The significance of the treatment effect for secukinumab at different analysis visits will be determined from the comparison to placebo.

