3.1 Determination of sample size

This study was designed using data for abatacept in the APPRAISE study (RA study to assess early response to abatacept + MTX ([D'Agostino et al, 2016](#)), to test the superiority of secukinumab compared to placebo at the 5% significance level using a 2-sided test. Assuming a difference in the mean change from Baseline at Week 12 in OMERACT global PDUS score of -5.8 with a pooled standard deviation of 13.2, 218 patients in total (109 patients per arm) were estimated to achieve a power of 90% ([EAST 6](#)).

A blinded SSR was performed once the first 60 patients completed the Week 12 visit to evaluate the assumptions used in the sample size calculations. The statistical test for the primary endpoint has been changed from a 2-sided to a 1-sided test.

The first 60 patients to reach Week 12 have a pooled mean change from Baseline at Week 12 in OMERACT global PDUS score of -5.25 with a pooled standard deviation of 9.527. Using the estimated placebo effect of roughly 50% of secukinumab based on data from the FUTURE 2 study (CAIN457F2312) as in the original sample size calculation, the pooled PDUS score change of -5.25 translates to an assumed change of -7.000 and -3.500 for the secukinumab and placebo group, respectively, providing a difference of 3.500 between the groups. Adapting the original sample size calculation to be 1-sided with the power relaxed to 80%, 184 patients in total (92 patients per arm) are required ([EAST 6](#)).

At the time of the blinded sample size calculation, 72 patients were available who had reached their Week 12 visit, to provide the most accurate estimation, all data available were considered i.e. the first 72 patients as opposed to the first 60 patients. Using all available data a difference in the mean change from Baseline at Week 12 in OMERACT global PDUSscore of 4.352 was observed with a pooled standard deviation of 9.822. At the 5% significance level using a 1sided test, 126 patients are needed to achieve a power of 80% ([EAST 6](#)).

The 2 calculations produce a sample size range of 127-185 patients; thus, the sample size will be adjusted to a new target of 164 patients in total (82 patients per arm). This is mid-

way point of the range plus a 5% adjustment based on the observed drop-out rate of patients prior to Week 12 observed at the time of this calculation.

For the secondary variables:

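### The primary GLOESS MMRM imposes one baseline slope on all visits; if the slope differs by visit, precision at Week 12 is lost, and a baseline-by-visit term would recover it cheaply

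*SAP*

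**What the plan says.** SAP 2.5.2 describes the primary MMRM with treatment regimen, "center and analysis visit as factors and weight and baseline GLOESS as continuous covariates". The only interaction is stated next: "Treatment by analysis visit will be included as an interaction term in the model". SAP 5.5.1 writes the same model as a formula: "Change from baseline in GLOESS = Treatment + center + analysis visit + weight + baseline GLOESS + Treatment * analysis visit". The covariance is unstructured, with compound symmetry as the fallback. The output is by visit: "95% confidence interval around the difference and 1-sided p-value will be calculated for each visit". H1 in SAP 2.6.2 concerns the change from Baseline to Week 12.

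The SPARCC model for H4 (SAP 2.6.2) is built the same way, with treatment and visit "as factors and baseline weight and SPARCC score as continuous covariates" and treatment by visit as its only interaction. The secondary model for GLOESS at Week 8 and the enthesitis score (SAP 2.7.2) also has baseline as a main effect only.

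The two descriptions of the primary model agree with each other, so there is no contradiction to resolve. The point concerns the choice of model.

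**The concern.** For a change score, the slope on baseline at visit t is cov(Y_t, Y_0)/var(Y_0) - 1. If the correlation with baseline falls as time passes and the SD does not rise, this slope becomes more negative at later visits. A model with a single slope then settles on a compromise weighted towards the visits with the smallest residual variance. When those are the early visits, the compromise is too shallow for Week 12, and baseline variation that could have been removed stays in the Week 12 residual.

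Week 12 is the visit named in H1, and the hierarchy in SAP 2.6.2 stops if H1 is not rejected. The trial has also lowered its power target from 90% to 80% for enrolment reasons (SAP 2.15). Precision available from a baseline that is already measured is therefore worth having.

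**Working it through.** **Step 1. The plan's own figures.** Inputs are from SAP 3.1. Patients per arm = 2(z_alpha + z_power)^2 SD^2 / difference^2.

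| Calculation | Difference | SD | Test, power | Per arm | Total |
|---|---|---|---|---|---|
| Original | 5.8 | 13.2 | 2-sided 5%, 90% | 108.8, so 109 | 218 |
| First 60 patients | 3.5 | 9.527 | 1-sided 5%, 80% | 91.6, so 92 | 184 |
| First 72 patients | 4.352 | 9.822 | 1-sided 5%, 80% | 63.0, so 63 | 126 |

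All three totals reproduce. The midpoint of the stated range 127-185 is 156, and 156 x 1.05 = 163.8, so 164.

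The re-estimation uses the SD of the raw change ("PDUSscore of 4.352 was observed with a pooled standard deviation of 9.822"), so the sample size takes no credit for baseline adjustment. With 5% drop-out, 82 x 0.95 gives about 78 completers per arm. On the raw SD:
- Difference 4.352: SE = 9.822 x sqrt(2/78) = 1.573, and power = Phi(4.352/1.573 - 1.645) = 86.9%.
- Difference 3.5: SE = 9.527 x sqrt(2/78) = 1.526, and power = Phi(3.5/1.526 - 1.645) = 74.2%.

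**Step 2. Formula for the loss.** Let beta be the vector of true per-visit slopes, S0 the residual covariance with visit-specific slopes, and Vx the baseline variance. The common-slope model converges to

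b = (1'S^-1 beta)/(1'S^-1 1), with S = S0 + Vx(beta - b)(beta - b)', iterated until stable.

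Treatment by visit is saturated, so the Week 12 treatment variance is proportional to the Week 12 diagonal element of S. Hence

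inflation = 1 + (beta_12 - b)^2 Vx / S0[12,12].

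This assumes complete data and ignores center and weight.

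**Step 3. Middle case (all inputs assumed).** Scans at Weeks 2, 4, 8 and 12; SD constant at 1; correlation between two visits 0.90 x exp(-0.04 x weeks apart).
- Slopes 0.90 x exp(-0.04t) - 1: Week 2 -0.169, Week 4 -0.233, Week 8 -0.346, Week 12 -0.443.
- Week 12 residual variance with its own slope: 1 - 0.557^2 = 0.690.
- Common slope: -0.233.
- Inflation: 1 + (-0.443 + 0.233)^2/0.690 = 1.064. In patients, 164 x (1 - 1/1.064) = about 10.
- Unadjusted variance of change: 2(1 - 0.557) = 0.886. With the common slope it is 0.734, so the planned model already secures (0.886 - 0.734)/(0.886 - 0.690) = 78% of the available reduction.

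**Step 4. Range by schedule.** Correlation decay 0.02-0.06 per week, reliability 0.80-0.95, SD constant or falling 20% by Week 12.

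| Assumed scan weeks | Week 12 variance inflation |
|---|---|
| 8, 12 | 0.1-1.2% |
| 4, 8, 12 | 1-8% |
| 2, 4, 8, 12 | 1-19% |
| 1, 2, 4, 8, 12 | 2-31% |

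**Step 5. A second set of assumptions.** Here the Week 12 SD of change is fixed at 9.822, scans are at Weeks 1, 2, 4, 8 and 12, baseline SD is 8-16, residual correlation is 0.5-0.7, and the visit SD is constant or growing. The variance ratios (common slope over visit-specific) are analytic. Power is simulated: 2,000 trials per scenario, 78 per arm, difference 4.352, baseline SD 12.

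| Slopes, first visit to Week 12 | Variance ratio | Power, common vs by-visit |
|---|---|---|
| Flat | 1.00 | 89.5% vs 89.6% |
| -0.15 to -0.30 | 1.00-1.09 | 89.7% vs 90.6% |
| -0.10 to -0.40 | 1.01-1.40 | 93.2% vs 93.8% (constant SD); 90.6% vs 92.8% (growing SD) |
| -0.05 to -0.50 | 1.01-1.49 | 89.0% vs 96.2% (growing SD) |

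Under no treatment effect, the common-slope model rejected in 4.6%-5.1% of trials at the 1-sided 5% level, and its estimates showed no bias. The by-visit model lost no power in any simulated scenario, including flat slopes.

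**The case against.** The strongest reply is that a prespecified common-slope MMRM is valid and internally consistent, and that every input to the size of the loss is assumed. That stands. The SAP gives no baseline SD, no correlation of baseline with change and no per-visit slope. For GLOESS before Week 24 it names only Weeks 8 and 12 as endpoint visits, and with those two scans alone the loss is negligible. The actual schedule would be in the protocol, which is not at hand.

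The target is also not wholly settled. SAP 2.5.1 and 2.5.2 speak of change over 12 weeks. If that meant the average over visits, the Step 4 assumptions give only 0-6%, and 1.4% in the middle case. H1 names Baseline to Week 12, so I have taken that contrast. SAP 2.5.4 plans sensitivity analyses on model assumptions, partly redacted; they might touch this point but would not change the primary model.

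A reader might infer four stronger things, none of them supported:
- *The test is biased or its error rate inflated.* The simulation shows neither.
- *The trial falls short of its planned power for this reason.* Sizing used the raw SD. Even in the worst scenarios examined, power at 4.352 stays at about 86.6% or more, against 86.9% on the raw SD.
- *Early slopes are near 0.* Measurement error produces regression to the mean at once. The middle case already has -0.17 at Week 2.
- *Patients without a Week 12 value are materially mispredicted.* This was not quantified, since the calculations assume complete data; drop-out was about 5%.

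The size for SPARCC, a bounded 0-16 count, was not computed either.

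**Conclusion.** The point holds as a conditional efficiency gain. The model constrains the baseline effect to be equal across visits without a stated reason, while leaving treatment and covariance free. If the slopes differ by visit, Week 12 precision is forgone. The loss runs from nil (flat slopes), or about 0.1-1% (Weeks 8 and 12 only), through 1-8% (Weeks 4, 8, 12), to larger values if there are earlier scans, with about 6% as a middle case. These figures depend on the assumed schedule, correlation decay, reliability and SD pattern. The SAP's analysis is valid as written. The reason to change it is that the slopes cannot be known in advance, and allowing them to differ costs almost nothing.

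**What to change.** Add baseline GLOESS * analysis visit to the model in SAP 2.5.2 and 5.5.1. Add the matching baseline-by-visit term to the SPARCC model (2.6.2) and the secondary models (2.7.2), so that all the MMRMs share one form. The Week 12 treatment difference keeps its meaning.

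The cost is a wording change and (number of visits - 1) degrees of freedom per model: 1 with two visits, 3 with four, 4 with five. The change should be fixed before the Week 12 treatment codes are opened. After that it could serve only as a labelled sensitivity analysis.

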2.1 Data analysis general information

The analysis outlined in this document will be performed by Novartis using SAS version 9.3 or higher software. All analyses outlined will also be performed by Novartis.

Comparative efficacy analyses (i.e. inferential efficacy comparisons with placebo) will focus on the time period when both active drug and the placebo are given in a manner suitable for making comparisons (e.g. double-blind). For AIN457F2354 this is the first 12-weeks of treatment. Comparative efficacy will be performed based on the FAS population using the randomized treatment. After week 12, the active secukinumab regimens will be compared using confidence intervals on the FAS population using treatment sequence. These treatment sequences represent the treatment combinations the subjects experience over the course of the entire trial in case of treatment switch at week 12.

The Week 3 efficacy assessment was removed from the study assessments in Protocol Amendment 2. Statistical comparisons at week 3 will not be presented due to the low number of subjects enrolled prior to this amendment.

Summary statistics for continuous variables will include N, mean, standard deviation, minimum, lower quartile, median, upper quartile and maximum values. Summary statistics for binary or discrete variables will be presented in contingency tables and will include absolute and relative frequencies.

The statistical analysis planned for the primary and secondary objectives are clearly stated, if not otherwise specified 95% confidence intervals may be presented along with point estimates and p-values will be presented as 1-sided.

Data analyses and summaries will be performed by treatment group (Secukinumab 150mg + 300 mg and Placebo) for baseline measurements, efficacy and safety data captured within the placebo-controlled period and for adverse events throughout the treatment periods.

Analyses of all efficacy and non-AE safety parameters for the treatment periods will be performed by treatment sequence and results presented for the following groups: secukinumab (150 mg + 300 mg), placebo – secukinumab (150 mg + 300 mg).

All listings will be presented by treatment sequence for efficacy and non-AE safety and by treatment for baseline and AE listings.

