2.6.2 Statistical hypothesis, model, and method of analysis

The following null hypotheses will be included in the testing strategy and type-I-errors will be set such that a family-wise type-I-error of 5% is kept:

Primary objective:

- H_1 : secukinumab s.c. is not different to placebo regimen with respect to the change in GLOESS from Baseline to Week 12.

[figure not shown]
See section 2.5.2 for details.

Key secondary objectives:

- H_2 : secukinumab is not different to placebo regimen with respect to ACR 20 response at Week 12.
- H_3 : secukinumab s.c. is not different to placebo regimen with respect to ACR 50 response at Week 12.
- H_4 : secukinumab s.c. is not different to placebo regimen with respect to the change in SPARCC enthesitis index from Baseline to Week 12.

No hypotheses other than H_1 to H_4 will be considered. The family wise error will be set to $\alpha=5\%$ (1-sided). The graphical approach of Bretz ([Bretz et al 2009](#)) for sequentially rejective testing procedures is used to illustrate the hierarchical testing strategy ([Figure 1](#)).

Figure 1 Testing strategy

The family-wise error will be set to $\alpha = 5\%$ (1-sided). H_1 is tested at α (1-sided). The following hypotheses will be tested sequentially and are included in the hierarchical testing strategy and type-I-errors will be set such that a family-wise type-I-error of 5% is kept:

The testing sequence will continue to H_2 at α (1-sided) only if H_1 has been rejected.

Similarly, the testing sequence will continue to H_3 at α (1-sided) only if H_2 has been rejected. This process will continue as each hypothesis is rejected up to H_4 .

Of note, in the description above, rejection of a hypothesis refers to rejection of the 1-sided hypothesis; however, the level of a rejected hypothesis is only passed on

(according to the graphical procedure) for the test of another hypothesis if the treatment effect is in favor of secukinumab.

ACR 20 at Week 12

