5.5.2 Key secondary analysis

The key secondary objectives:

- H_2 : secukinumab is not different to placebo regimen with respect to ACR 20 response at Week 12.
- H_3 : secukinumab s.c. is not different to placebo regimen with respect to ACR 50 response at Week 12.
- H_4 : secukinumab s.c. is not different to placebo regimen with respect to the change in SPARCC enthesitis index from Baseline to Week 12.

H_2 will be tested as follows:-

ACR 20 at Week 12 = Treatment + weight.

The procedure PROC LOGISTIC will be used to perform the logistic regression analysis. Treatment regimen will be set as a class variable. The model statement will be based on the formula outlined above. Reference coding will be used in the model. The odds ratios will be computed for comparison of secukinumab versus placebo using the logistic regression model fitted. If the initial model does not converge Firth's penalized maximum likelihood estimation method will be used.

H_3 will be analysed analogous to H_2 above.

H_4 will be analysed analogous to the primary efficacy variable.

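### Does a 95% confidence interval beside a 1-sided 5% test of H1 call for a change to the plan?

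*SAP*

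**What the plan says.** Section 2.6.2 sets the family-wise error at 5%, 1-sided: "type-I-errors will be set such that a family-wise type-I-error of 5% is kept". H1 is tested at the full level, which then passes to H2, H3 and H4 in fixed order, each step requiring the previous rejection. The section also settles what counts as a rejection: "rejection of a hypothesis refers to rejection of the 1-sided hypothesis". The level is passed on only if the effect favours secukinumab.

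The planned outputs are as follows.

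- **H1 (GLOESS).** Section 5.5.1 commits to an interval and a p-value from the MMRM: "95% confidence interval around the difference and 1-sided p-value will be calculated for each visit".
- **H4 (SPARCC).** Section 5.5.2 says that it "will be analysed analogous to the primary efficacy variable", so the same pairing follows by inference. The SPARCC text in 2.6.2 names no interval.
- **H2 and H3 (ACR 20, ACR 50).** Sections 2.6.2 and 5.5.2 call for odds ratios and fix no interval level.
- **General default.** Section 2.1 says "95% confidence intervals may be presented along with point estimates and p-values will be presented as 1-sided". For intervals this is permissive.

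Section 3.1 describes the initial design as a 2-sided 5% test and then reports the change: "The statistical test for the primary endpoint has been changed from a 2-sided to a 1-sided test". It gives the revised sample sizes at 1-sided 5%. The SAP plans neither a 90% interval nor a one-sided 95% bound, and it does not comment on how to read the 95% interval beside the test.

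**The concern.** A test and the interval printed next to it are usually expected to agree: the test rejects exactly when the interval excludes zero. A two-sided 95% interval has that relation with a 2-sided 5% test, or equivalently a 1-sided 2.5% test. The test that decides H1 is 1-sided 5%, and its matching interval is a two-sided 90% interval or a one-sided 95% bound.

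It looks as though the test was changed during the trial and the interval was left as it was. If the result fell in the gap, the report would declare success on the primary endpoint and move on to ACR 20, with an interval for the primary difference that crosses zero. A reader could take this as a contradiction. A reader could also miss that the chance of a false claim for secukinumab on H1 is now 5%, against 2.5% under the initial 2-sided 5% test.

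**Working it through.** **Inputs, all from section 3.1 unless stated.** Initial design: difference 5.8, SD 13.2, power 90%, total 218. Re-estimation on 60 patients: difference 3.500, SD 9.527, power 80%, total 184. Re-estimation on 72 patients: difference 4.352, SD 9.822, power 80%, total 126. Final target: 82 per arm. Level: 5%, 1-sided (section 2.6.2). The interval is taken as two-sided, which is the natural reading although the SAP does not use the word.

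**Step 1: is the 1-sided 5% level meant, or a slip?** Total N = 4 × ((z₁₋ₐ + z_power) × SD / d)².

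| d / SD / power | a = 0.05 | a = 0.025 | SAP |
|---|---|---|---|
| 5.8 / 13.2 / 90% | 177.4 | 217.7 | 218 |
| 3.5 / 9.527 / 80% | 183.2 | 232.6 | 184 |
| 4.352 / 9.822 / 80% | 126.0 | 159.9 | 126 |

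The SAP's three figures are reproduced. The initial one fits 2-sided 5% and both re-estimated ones fit 1-sided 5%. The level is deliberate and is used consistently in 2.6.2 and 3.1.

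**Step 2: where do test and interval disagree?** The test rejects when the estimate is more than 1.645 SE in favour of secukinumab. The two-sided 95% interval excludes zero beyond 1.960 SE. They disagree between the two, which is a 1-sided p of 0.025 to 0.05.

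With SD 9.527, SE = 9.527 × √(2/82) = 1.488, so the band is an observed difference of 2.45 to 2.92 points. With SD 9.822, SE = 1.534 and the band is 2.52 to 3.01.

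Illustration: a difference of −2.68 (1.80 × 1.488) gives a 1-sided p of 0.036, a 95% interval of −2.68 ± 2.92 = −5.59 to 0.24 (limits from unrounded values), and a 90% interval of −2.68 ± 2.45 = −5.13 to −0.23.

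**Step 3: how likely is that?** P = P(Z > 1.645 − d/SE) − P(Z > 1.960 − d/SE), at 82 per arm.

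- 60-patient estimate: 0.760 − 0.653 = 0.108 after rounding, about 14% of all rejections.
- 72-patient estimate: 0.883 − 0.810 = 0.074 after rounding, about 8% of all rejections.
- Null: 0.05 − 0.025 = 0.025.

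At 78 per arm, allowing for about 5% drop-out, the first two become 11.1% and 7.9%. These figures ignore the MMRM covariates, and the SAP does not say how much variance the covariates explain. If they explained 25% (assumption), the figures at 82 per arm would be 8.3% and 4.3%. At 50% (assumption), they would be 4.0% and 1.1%.

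**Step 4: what would a result in the band change?** By section 2.6.2, H1 is rejected and H2 is tested. The interval plays no part. The error rate of the sequence stays at 1-sided 5%, and the sample size in 3.1 stays as it is. The two statements are also compatible: p = 0.036 says that the 1-sided 5% test rejects, and an upper 95% limit of 0.24 says that a 1-sided 2.5% test would not.

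**Step 5: what would a matching interval add?** With normal quantiles, the half-width of the 90% interval is 1.645/1.960 = 0.839 times that of the 95% interval. In the illustration, 2.92 × 0.839 = 2.45. Anyone holding the estimate and the planned interval already has the matching one, with a small adjustment if t quantiles are used.

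**The case for a change.** The strongest case for a change has three parts.

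First, the mismatch is firm for H1: section 5.5.1 commits to the interval beside the deciding p-value and never calls it descriptive. This stands as a description of the SAP. But a test level and an estimation level may differ, and a 95% interval is a legitimate output in its own right. It is also the stricter of the two displays, so a reader who judged by it would claim less than the test allows, not more.

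Second, the re-estimated design can land in the band with a probability that is not negligible. The arithmetic is right. The size depends on covariate effects that the SAP does not give (1.1% to 10.8% at 82 per arm over the values tried), and at any size the consequence is one of presentation.

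Third, the reader is said not to learn that the false-claim rate rose from 2.5% to 5%. This does not stand. Section 2.6.2 states the 1-sided 5% level more than once, and section 3.1 reports the initial 2-sided 5% test, the switch, and the new level. That 1-sided 5% corresponds to 2-sided 10% is an identity; leaving it out is not an error.

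The reach is also narrower than all four hypotheses. H4 is covered only by analogy. For H2 and H3 no interval level is fixed, so no mismatch is planned there.

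**Conclusion.** No change is needed. For H1, and for H4 by analogy, the SAP pairs a 1-sided 5% test with a 95% interval. A 1-sided p between 0.025 and 0.05 would then sit beside an interval that includes zero. The chance is about 7% to 11% under the section 3.1 assumptions at 82 per arm, lower if covariates explain much of the variance, and 2.5% under the null. These figures rest on a two-sample normal approximation and on reading the interval as two-sided.

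The test and the interval are each valid, the decision rule names the test alone, and the level and its change are disclosed. Another interval would alter no decision, error rate or sample size, and it follows from the planned output by rescaling. If a result did fall in the band, a footnote in the report saying that the 1-sided test decides would be enough; the analysts can supply it without amending the SAP.
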